 [REDACTED] FSH=follicle stimulating hormone; HBsAg=hepatitis B surface antigen; HBV=hepatitis B virus; HCV-Ab=hepatitis C virus antibody; HS=hidradenitis suppurativa clinical response; HIV=human immunodeficiency virus; HS=hidradenitis suppurativa; [REDACTED] hs-CRP=high-sensitivity C-reactive protein; IgG=immunoglobulin G; IgM anti-HBc=immunoglobulin M antibody to hepatitis B core antigen; IHS4=International Hidradenitis Suppurativa Severity Score System; IMP=Investigational Medicinal Product; IRT=interactive response technology; OX40L=OX40-Ligand; PD=pharmacodynamic(s); PK=pharmacokinetic(s); [REDACTED]; SAA=serum amyloid A; SAE=serious adverse event; SC=subcutaneous(ly); TB=tuberculosis; [REDACTED]  
 | V=visit; W=week; WOCBP=women of childbearing potential.

- a When several assessments take place at the same time, the following order should be respected: questionnaires, ECG, followed by vital signs, AE reporting, prior and concomitant medications, daily diary review, blood sampling, physical examination, lesion intervention if needed, HS clinical parameters, skin biopsy, and IMP administration.
- b A maximum of 28 days is required depending on participants' prior and concomitant medications. Randomization of the participant must take these constraints into consideration.
- c All visits are done on-site except if home nursing is arranged for visits at Week 18, 22, or 26. Participants in Denmark will not have home nursing, please refer to [Section 10.8.1.2](#).
- d Participants who discontinue IMP treatment prior to completing the 28-week treatment period and 8-week Follow-up Period will be evaluated as soon as possible at the individual participant's EOT Visit, using procedures as planned for the EOT Visit at Week 28 (Visit 16). At their EOT Visit, participants will resume their HS medications or other appropriate therapy as needed per Investigator discretion after the EOT study assessments have been performed and will enter the 8-week safety Follow-up Period, concluding with EOS Visit (Visit 17).
- e The study visits occur on the planned dates (relative to the first IMP), as scheduled.
- f Visits at Week 18, 22, and 26 may be performed with a home nursing service.
- g To qualify for randomization all inclusion criteria and none of the exclusion criteria are met by the participant.
- h Update inclusion/exclusion criteria, medical and surgical history, and prior and concomitant medications information to assure participant eligibility.

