AE=adverse event; Ab=antibody; AN=abscess and inflammatory nodule; ANC=absolute neutrophil count; anti-HBc=hepatitis B core antibody; anti-HBs=hepatitis B surface antibody; COVID-19=coronavirus disease 2019; CRP=C-reactive protein; C-SSRS= Columbia-Suicide Severity Rating Scale; D=day; ECG=electrocardiogram; eCRF=electronic case report form; EOT=end of treatment; EOS=end of study; [REDACTED] FSH=follicle stimulating hormone; HBsAg=hepatitis B surface antigen; HBV=hepatitis B virus; HCV-Ab=hepatitis C virus antibody; HS=hidradenitis suppurativa clinical response; HIV=human immunodeficiency virus; HS=hidradenitis suppurativa; [REDACTED]; hs-CRP=high-sensitivity C-reactive protein; IgG=immunoglobulin G; IgM anti-HBc=immunoglobulin M antibody to hepatitis B core antigen; IHS4=International Hidradenitis Suppurativa Severity Score System; IMP=Investigational Medicinal Product; IRT=interactive response technology; OX40L=OX40-Ligand; PD=pharmacodynamic(s); PK=pharmacokinetic(s); [REDACTED]; SAA=serum amyloid A; SAE=serious adverse event; SC=subcutaneous(ly); TB=tuberculosis; [REDACTED] V=visit; W=week; WOCBP=women of childbearing potential.

a All participants in the US will be assessed for response at the Week 20 visit based on the HS Clinical Parameters. Response will be defined as ≥50% reduction from Baseline in the total AN count, with no increase from Baseline in abscess or draining tunnel count at Week 20. For non-responders, they will not continue in Period B and immediately begin procedures for the EOT visit as depicted in the SOA. For responders, they will continue in Period B and perform assessments for the Week 20 visit as depicted in the SOA.

- b* At the Week 20 visit, HS Clinical Parameters will be performed prior to any assessment to assess treatment response. At all other visits, when several assessments take place at the same time, the following order should be respected: questionnaires, ECG, followed by vital signs, AE reporting, prior and concomitant medications, daily diary review, blood sampling, physical examination, lesion intervention if needed, HS clinical parameters, skin biopsy, and IMP administration.
- c* A maximum of 28 days is required depending on participants' prior and concomitant medications. Randomization of the participant must take these constraints into consideration.
- d* All visits are done on-site except if home nursing is arranged for visits at Week 18, 22, or 26.

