- cc Hidradenitis Suppurativa Clinical Parameters will be performed at each designated study visit and must address all relevant anatomical regions in each participant; the number, location, longest distance between relevant lesions, and whether the lesions are separated by normal-appearing skin will be measured in each anatomical area; Hurley Stage is included as an assessment performed during the HS clinical parameters; Hidradenitis Suppurativa Physician's Global Assessment is included as an assessment performed during the HS clinical parameters. The site is responsible for counting lesions that received intervention as permanently present in the lesion counts from the date of the intervention. The data collected from the HS clinical parameters will be used for the derivation of the HiSCR50, HiSCR75, HiSCR90, IHS4, AN count, Hidradenitis Suppurativa Physician's Global Assessment, raw counts, and disease flares. For each participant it is recommended that the HS Clinical Parameters is assessed by the same Investigator during the entire study if possible.
- dd [REDACTED]
- ee The participant should complete the questionnaire before site personnel perform any clinic assessments and before any interaction with the site personnel has occurred to avoid biasing the participant's response.
- ff Number of samples (tubes) and quantity of biological samples needed for each assessment can be found in the laboratory manual.
- gg Up to 4 hours prior to IMP administration.
- hh PD biomarkers will include serum TNF and serum OX40L.
- ii Optional assessment with skin biopsies at Baseline (Visit 2) and Week 16 (Visit 10) will be performed. Participants without history of hypertrophic or keloid scarring as assessed by the Investigator through participant interview and review of medical history can choose whether they would like to participate in optional assessment. If they consent to participate, the participants will have one lesional biopsy of an inflammatory nodule and one non-lesional biopsy at Baseline (Visit 2) and Week 16 (Visit 10) (for a total of 4 biopsies). Biopsy is to be performed after HS clinical parameters, but before IMP administration at study visit. Sutures may be placed per the discretion of the Investigator. Participants will be scheduled for an additional visit 1 week after skin biopsy for suture removal if sutures are placed per the discretion of the Investigator. Sample will be processed per instructions in the laboratory manual.

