### **10.8.2 United States (US)**

At the Week 20 visit, all participants in the US will be assessed for response defined as  $\geq 50\%$  reduction from Baseline in the total AN count, with no increase from Baseline in abscess or draining tunnel count. Participants who meet the definition of response will continue in the open-label period to receive SAR442970 150 mg Q2W up to the Week 26 visit. Thereafter, responders will move to Period C which will commence with an end of treatment visit (approximately 2 weeks after the last IMP administration) and after 8 weeks conclude with an EOS Visit. Participants who do not meet the definition of response at the Week 20 visit will immediately begin Period C. The Week 20 visit will be the EOT visit for non-responders (SAR442970 will not be administered at this visit), and the EOS visit will be scheduled approximately 8 weeks after the EOT visit.

All participants in the US who complete the Week 4, Week 8, Week 12, Week 20, and Week 24 visit will have a complete physical examination at these visits. All participants in the US who complete the Week 4, Week 12, Week 20, and Week 24 visit will have laboratory testing at these visits. For details, please refer to [Section 1.3.2](#).

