A measurement (scheduled or unscheduled) will be used if it is available and measurement date is within the analysis window.

After applying these time windows, if multiple assessments are associated to the same time point, the closest from the targeted study day will be used. If the difference is a tie, the value after the targeted study day will be used. If multiple valid values exist within a same day, then the first value of the day will be selected. For procedures planned on Visit 2, if it is done on the same date as the first IMP injection but the performance time is missing, it will belong to the Visit 2 window.

If there is no measurement for a given parameter in an analysis window, data will be considered missing for the corresponding visit.

Table 12 - Analysis window definition for safety analysis

Analysis visits	Targeted study day ^a	Time window				
		Vital signs	Fasting lipid panel	Non-fasting laboratory tests	Urinalysis	12-lead ECG
Period A						
Screening	-28 to -14	<-14	<-14	<-14	<-14	<-14
Baseline	1	-14 - 1	-14 - 1	-14 - 1	-14 - 1	-14 - 1
Week 2	15	2 - 21	2 - 21	2 - 21	2 - 21	2 - 21
Week 4	29	22 - 35	22 - 35	22 - 35	22 - 35	22 - 35
Week 6	43	36 - 49	36 - 49	36 - 49	36 - 49	36 - 49
Week 8	57	50 - 63	50 - 63	50 - 63	50 - 63	50 - 63
Week 10	71	64 - 77	64 - 77	64 - 77	64 - 77	64 - 77
Week 12	85	78 - 91	78 - 91	78 - 91	78 - 91	78 - 91
Week 14	99	92 - 105	92 - 105	92 - 105	92 - 105	92 - 105
Week 16	113	106 - D ^b	106 - D ^b	106 - D ^b	106 - D ^b	106 - D ^b
Period B						
Week 18	15	2 - 21	2 - 21	2 - 21	2 - 21	2 - 21
Week 20	29	22 - 35	22 - 35	22 - 35	22 - 35	22 - 35
Week 22	43	36 - 49	36 - 49	36 - 49	36 - 49	36 - 49
Week 24	57	50 - 63	50 - 63	50 - 63	50 - 63	50 - 63
Week 26	71	64 - 77	64 - 77	64 - 77	64 - 77	64 - 77
Week 28	85	78 - 112	78 - 112	78 - 112	78 - 112	78 - 112
Week 36	141	>112	>112	>112	>112	>112

a Day 1 in Period A is the day of the first blinded IMP administration (or the day of randomization for participant not exposed).

Day 1 in Period B is the day of the first open-label IMP administration.

b Last window in Period A is the 1st dose of open-label IMP administration.

Table 13 - Analysis window definition for efficacy endpoints

Analysis visit	Targeted study day ^a	Time windows			
		HS clinical parameters	Dermatology Life Quality Index	Hidradenitis Suppurativa Quality of Life	
Period A					
Screening	-28 to -14	<-14	<-14		<-14
Baseline	1	-14 - 1	-14 - 1		-14 - 1
Week 2	15	2 - 21	2 - 21		2 - 21

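### At US Week 20, footnote b puts the lesion count ahead of the questionnaires and footnote ee forbids it; the firm case is the EOT questionnaire of US non-responders

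*Protocol*

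**What the plan says.** Protocol 1.3.2 (US flowchart), footnote b: "At the Week 20 visit, HS Clinical Parameters will be performed prior to any assessment to assess treatment response". The usual sequence is then kept for the remaining visits: "At all other visits, when several assessments take place at the same time, the following order should be respected: questionnaires, ECG" and so on, with the HS Clinical Parameters near the end.

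Footnote ee of the same flowchart: "The participant should complete the questionnaire before site personnel perform any clinic assessments and before any interaction with the site personnel has occurred". Its stated reason is "to avoid biasing the participant's response". It names no visit as an exception.

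The Week 20 count has an immediate consequence in the US. Footnote a: "For non-responders, they will not continue in Period B and immediately begin procedures for the EOT visit as depicted in the SOA". Protocol 10.8.2 agrees: "The Week 20 visit will be the EOT visit for non-responders (SAR442970 will not be administered at this visit").

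The flowchart for all other countries (Protocol 1.3.1, footnote a) makes no Week 20 exception: "When several assessments take place at the same time, the following order should be respected: questionnaires, ECG, followed by vital signs".

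In the SAP, Appendix 4 has "Table 13 - Analysis window definition for efficacy endpoints", with columns for the HS Clinical Parameters, the DLQI and the HiSQOL and a window labelled Week 20. SAP 2.10 gives the time points of one DLQI endpoint as Weeks 16 and 28. SAP 2.5 makes Period B efficacy descriptive, without testing.

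**The concern.** Footnotes b and ee give opposite orders for the same visit, and neither refers to the other. A questionnaire completed at US Week 20 breaks one of them whichever way the site acts.

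The order matters more at this visit than at others. In the US the Week 20 count decides whether open-label treatment goes on. A participant who answers quality-of-life items after that count has already been examined by staff and may know the outcome. The sponsor's own reason for putting questionnaires first is to keep such influences out of the answers. Non-US participants answer first, so scores collected under the two orders would be summarised together.

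**Working it through.** No arithmetic drives this point, and the plan states no figure to reproduce. The check sets the passages side by side.

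**1. Can both rules be followed?** Footnote b puts the lesion count before every other assessment at Week 20 and does not exempt questionnaires. Footnote ee puts the questionnaire before every clinic assessment and does not exempt Week 20. They are incompatible for any questionnaire given at that visit. Footnote b also limits its ordered list to the other visits, so after the count no order is set at US Week 20.

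**2. Who is firmly affected?**
- SAP 2.10 gives a DLQI endpoint at Weeks 16 and 28.
- Protocol 1.3.1, footnote d, identifies Week 28 as the planned EOT visit, so the DLQI is an EOT procedure.
- US non-responders carry out EOT procedures at Week 20 (Protocol 1.3.2, footnote a; 10.8.2).
- Under footnote b, those procedures come after the count.

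So the EOT DLQI of a US non-responder follows the count. This assumes that the DLQI is one of the questionnaires governed by footnote ee. The SAP supports that: it windows the DLQI with the visit-based measures in Table 13, not with the daily diaries in Table 14.

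**3. Are US responders affected too?** This cannot be settled. The flowchart rows for the questionnaires are redacted. Table 13 gives the DLQI and HiSQOL a Week 20 window of Period B Days 2 to 42, but a window does not prove collection. Table 15 gives the same Week 20 window to ADA, blood biomarkers and PD biomarkers, while SAP 2.8.2 and 2.8.3 list collection times for these without Week 20.

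**4. Where does a non-responder's score go?** The planned Week 16 and Week 20 visits are on Days 113 and 141. If open-label dosing starts at Week 16, Week 20 falls on Period B Day 141 − 113 + 1 = 29. With ±3 days at each visit the range is Day 23 to Day 35. All of it lies inside the Week 20 window (2–42) and outside the Week 28 window (beyond 70). The score therefore appears in the Week 20 summary, and the readable text of SAP 2.5 has no rule that carries it to Week 28.

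**5. Is it mixed with non-US data?** SAP 2.1 presents Period B by treatment sequence and overall, not by country. Any non-US Week 20 questionnaire, collected questionnaires-first, would be in the same summary.

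**6. What is not touched?** The primary endpoint and the Week 16 secondary efficacy endpoints precede this visit. Skin pain and itch come from a daily diary, intended for the evening, not from a clinic questionnaire.

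**The case against.** The best defence is that footnote b is a deliberate exception. It gives its purpose, restores the usual order for all other visits, and has a practical reason: the count tells staff whether to carry out the Week 20 or the EOT procedures. A specific visit rule can be read as overriding a general one, so sites have an instruction they can work with. That explains why footnote b exists. It does not remove the conflict, because footnote ee has no matching exception and the bias it guards against is not addressed.

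Two stronger readings are tempting. A reader might infer that every US participant is affected at Week 20. The documents do not show that, since the rows are redacted and the Table 13 window only suggests it. A reader might also infer that the scores are biased in a known direction, worse in those who stop and better in those who continue. No passage says when participants learn their status, so bias is possible but neither its presence nor its direction is documented.

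It is also fair to say that US and non-US Period B data differ anyway, because only US non-responders leave at Week 20. That limits what comparability the fix can restore, but it is no reason to add a further difference in how scores are collected.

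**Conclusion.** The conflict between footnotes b and ee is real and should be reconciled. It is firm for the EOT questionnaire of US non-responders, and conditional for US responders on questionnaires being scheduled at Week 20. The affected scores may be biased and are collected in a different order from the non-US scores summarised with them.

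The consequence is small: US participants only, one open-label visit, and exploratory data that are only described. The number of participants cannot be given, because the documents state neither US enrolment nor an expected Week 20 response rate. Nothing here bears on the trial's main efficacy conclusion. The case for acting is that the protocol sets aside its own safeguard at the visit where the count has the most direct consequence for the participant, and that restoring it costs very little.

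**What to change.** Amend footnote b so that at US Week 20 the participant first completes any questionnaire due at either the Week 20 or the EOT visit, then has the HS Clinical Parameters, then the remaining Week 20 or EOT assessments. Footnote ee then holds without exception. The response definition and its consequences stay as they are. Send sites a short memo, and state in the study report that US Week 20/EOT questionnaires already collected followed the other order.

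Cost: one footnote, one memo and one sentence in the report. The response decision comes a few minutes later. If a questionnaire turns out to be due only at EOT, US responders would complete one extra questionnaire at Week 20, because their status is not yet known when it is handed out.

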### Overall design synopsis:

This is a multinational, multi-center, randomized, double-blind, placebo-controlled, Phase 2a proof of concept study to evaluate the efficacy and safety of SAR442970 in adult participants with moderate to severe HS.

The intervention in the study includes investigational medicinal product (IMP) administration every 2 weeks (Q2W) to complete 28 weeks of treatment with SAR442970. The study is

composed of 3 parts: a double-blind, placebo-controlled period (Period A), followed by an open-label period (Period B), and then followed by a safety Follow-up Period (Period C).

Participants will receive SAR442970 150 milligrams (mg) or matching placebo Q2W at the Week 0 visit up to the Week 14 visit as part of Period A, the double-blind, placebo-controlled period. Beginning at the Week 16 visit, all participants will receive SAR442970 150 mg Q2W up to the visit prior to the individual participant's end of treatment (EOT) visit as part of Period B, the open-label period. Period C will be an 8-week safety Follow-up Period commencing with the End of Treatment (EOT) visit and concluding with the End of Study (EOS) visit. Participants will not be expected to receive more than 14 doses of SAR442970. [For participants in the US, response will be assessed at the Week 20 visit (see definition of response in [Section 4.1](#)). Responders at Week 20 will continue in Period B to complete the 12-week open-label period. Non-responders at Week 20 will move directly to the safety follow-up period (Period C) with the Week 20 visit serving as their EOT visit. No IMP will be administered to non-responders at their EOT visit at Week 20].

The target population of the study is participants with HS based on a history of signs and symptoms consistent with HS for at least 1 year prior to Baseline and demonstrating moderate to severe disease at Baseline as defined by HS lesions present in at least 2 distinct anatomic areas (eg, left and right axilla; or left axilla and left inguino-crural fold), one of which must be Hurley Stage II or Hurley Stage III, an abscess and inflammatory nodule (AN) count of  $\geq 3$ , a draining tunnel count  $\leq 20$ , and C-reactive protein (CRP) level of  $> 3$  mg/L.

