- v* All eligible participants will be treated for 28 weeks, receiving a SC administration of IMP or placebo every 2 weeks for the first 14 weeks based on randomization, and then starting at Week 16 (Visit 10) all participants will receive IMP every 2 weeks until the last dose is administered at Week 26 (Visit 15).
- w* Per Investigator discretion, participants may resume treatment for HS as needed (including, but not limited to oral and topical antibiotics, corticosteroids, opioid and non-opioid analgesics, spironolactone, finasteride, or metformin). Participants may also receive unlimited lesion intervention as needed per Investigator discretion.
- x* Vital signs, including body temperature (°C), heart rate (beats per minute), respiratory rate (breaths per minute), and systolic and diastolic blood pressure (mm Hg), will be measured at all visits detailed in the flowchart.
- y* Physical examination will include examination of skin, nasal cavities, eyes, ears, cardiovascular, respiratory, gastrointestinal, neurological, lymphatic, and musculoskeletal systems. A brief symptom-directed physical examination should be performed at other visits if, in the opinion of the Investigator, it is warranted by the participant's AE status or on review of symptoms and will include, at a minimum, assessments of the skin, cardiovascular system, and abdomen (liver and spleen). Height will be measured and recorded at the Screening Visit. Weight will also be measured and recorded at the Screening, Baseline, Week 16, and EOS Visit.
- z* For fasting lipid panel, participant must be fasting for 8 hours prior to laboratory testing (may consume water). If unable to fast, participant may consume a light meal. Labs drawn during non-fasting laboratory testing will include hematology and clinical chemistry only. For laboratory testing please see [Table 12](#).
- aa* Only for WOCBP: serum pregnancy test at Screening (Visit 1) and urine pregnancy tests at every visit from Baseline (Visit 2) to EOS (Visit 17). A negative result must be obtained at Screening (Visit 1) and at Baseline (Visit 2) prior to randomization. In case of positive urine test, the study treatment will be withheld and a serum pregnancy test to confirm the pregnancy should be performed as soon as possible. Pregnancy will lead to definitive treatment discontinuation in all cases.

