| Visit Label  | Screening                                       | Baseline  |           |   |           |           |           |           |           |            |                  |   |  |                  |   |                  | EOT e                             | EOS e  |
| Visit Weeks f   | W-4 to W0                                       | W0  | W2        | W4  | W6        | W8        | W10       | W12       | W14       | W16        | W18 g |   | W20  | W22 g | W24   | W26 g |  |   |
| Visit Days   | D-28 to D-1                                     | D1  | D15 (±3d) | D29 (±3d)   | D43 (±3d) | D57 (±3d) | D71 (±3d) | D85 (±3d) | D99 (±3d) | D113 (±3d) | D127 (±3d)       |   | D141 (±3d)                                       | D155 (±3d)       | D169 (±3d)  | D183 (±3d)       | (±3d)  | (±5d)   |
| Initiate Washout of HS and Non-HS Medications If Needed s | X   |   |           |   |           |           |           |           |           |            |                  |   |  |                  |   |                  |  |   |
| Daily Diary Introduction and Training t                   | X   |   |           |   |           |           |           |           |           |            |                  |   |  |                  |   |                  |  |   |
| Follow-Up Phone Call v                                    | X   |   |           |   |           |           |           |           |           |            |                  |   |  |                  |   |                  |  |   |
| Treatment   |   |   |           |   |           |           |           |           |           |            |                  |   |  |                  |   |                  |  |   |
| Call IRT   | X   | X   | X         | X   | X         | X         | X         | X         | X         | X          | X                |   | X  | X                | X   | X                | X  | X   |
| Randomization  |   | X h  |           |   |           |           |           |           |           |            |                  |   |  |                  |   |                  |  |   |
| IMP Administration w                                      |   | X   | X         | X   | X         | X         | X         | X         | X         | X          | X                |   | X  | X                | X   | X                |  |   |

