- e* Participants who discontinue IMP treatment prior to completing the treatment period and 8-week Follow-up Period will be evaluated as soon as possible at the individual participant's EOT Visit, using procedures as planned for the EOT Visit. At their EOT Visit, participants will resume their HS medications or other appropriate therapy as needed per Investigator discretion after the EOT study assessments have been performed and will enter the 8-week safety Follow-up Period, concluding with EOS Visit.
- f* The study visits occur on the planned dates (relative to the first IMP), as scheduled.
- g* Visits at Week 18, 22, and 26 may be performed with a home nursing service.
- h* To qualify for randomization all inclusion criteria and none of the exclusion criteria are met by the participant.
- i* Update inclusion/exclusion criteria, medical and surgical history, and prior and concomitant medications information to assure participant eligibility.
- j* Prior to randomization.
- k* Investigators must obtain a history of prior therapies used to treat HS, including antibiotics. The prior doses and reasons for discontinuation of antibiotic therapy will need to be recorded in the eCRF to verify eligibility. In the TNF-experienced population, Investigators will be asked to complete a questionnaire on the duration of anti-TNF therapy use as well as providing a description of the treatment response to anti-TNF therapy.
- l* Investigators will be asked to complete a questionnaire on participant's family history of HS in first-degree relatives (parents, siblings, and children) to be recorded in the eCRF.

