- r* COVID-19 molecular test (if COVID-19 testing is required per local guidelines to be determined for each site). It is strongly recommended that participants have completed required COVID-19 vaccination series (with booster[s]), inactivated influenza vaccination, and pneumococcal vaccination per local guidelines 14 days prior to Baseline (Visit 2). This recommendation applies to any other age and gender-specific appropriate non-live vaccination series as per local guidelines as well. If live vaccines are required as per local guidelines, these must be completed 12 weeks prior to Baseline.
- s* Please refer to [Table 4](#) – Prohibited therapy prior to Baseline for detailed description of required washout periods for various medications.
- t* Daily diary is used for daily recording of [REDACTED], participant daily analgesic use, and [REDACTED] from at minimum 4 days prior to Baseline (Visit 2) up to Week 28 (Visit 16). It should preferably be completed at about the same time every evening. It may also be used to document IMP administration if the participant receives IMP through home nursing.
- u* Diary for IMP administration must be completed to document IMP administration if participant receives IMP through home nursing.
- v* Sites are encouraged to contact participants 10 days prior to Baseline (Visit 2) to confirm compliance with daily pain collection and daily analgesic use in the daily diary.
- w* All eligible participants will be treated for up to 28 weeks, receiving a SC administration of IMP or placebo every 2 weeks for the first 14 weeks based on randomization, and then starting at Week 16 (Visit 10) all participants will receive IMP every 2 weeks until the last dose is administered at the individual participant's EOT visit.

- x Per Investigator discretion, participants may resume treatment for HS as needed (including, but not limited to oral and topical antibiotics, corticosteroids, opioid and non-opioid analgesics, spironolactone, finasteride, or metformin). Participants may also receive unlimited lesion intervention as needed per Investigator discretion.
- y Vital signs, including body temperature (°C), heart rate (beats per minute), respiratory rate (breaths per minute), and systolic and diastolic blood pressure (mm Hg), will be measured at all visits detailed in the flowchart.

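### US schedule footnote w puts the last IMP dose at the EOT visit, against every explicit statement of the last dosing visit elsewhere in the protocol and SAP

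*Protocol*

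**What the plan says.** Footnote w annotates the row labelled "IMP Administration w" in the US schedule (protocol section 1.3.2). It says that from Week 16 all participants receive IMP every two weeks "until the last dose is administered at the individual participant's EOT visit".

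The other places that fix the last dose are these:

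- **Synopsis, Overall design.** From Week 16, "all participants will receive SAR442970 150 mg Q2W up to the visit prior to" the EOT visit. The Synopsis brief summary and SAP section 1.1 say the same.
- **US non-responders.** The Synopsis states: "No IMP will be administered to non-responders at their EOT visit at Week 20". Section 10.8.2 repeats the prohibition.
- **US responders.** Section 10.8.2 ends dosing at Week 26 and places EOT about two weeks after the last dose. Section 4.2 also ends dosing at Week 26.
- **The annotated row.** It is marked at Weeks 0 to 26, and its EOT and EOS cells are blank. Footnote a sends Week 20 non-responders to that EOT column: they "immediately begin procedures for the EOT visit as depicted in the SOA".
- **Dose totals.** Section 4.1 allows up to 14 IMP doses. Table 6 gives 14 active doses in one arm, and 8 placebo plus 6 active in the other.
- **Non-US counterpart.** Footnote v in section 1.3.1 ends the equivalent sentence at Week 26.

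One other line is loose in the same direction as footnote w. Under Study interventions, the Synopsis gives the Period B regimen as running up to Week 28.

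**The concern.** The schedule is an operative document. Section 6.3 has study intervention dispensed at the visits that it lists, and section 8 makes adherence to it a requirement. A US site therefore has a footnote on the IMP row telling it to dose at EOT, and an appendix telling it not to.

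At stake is one unplanned dose of an investigational biologic per US participant who reaches a scheduled EOT visit. For Week 20 non-responders that dose would breach an explicit prohibition. It would be given at the visit where they are meant to leave treatment and where other HS therapy may resume.

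The footnote also cannot be met for participants who stop IMP early. Under footnote e they "will be evaluated as soon as possible at the individual participant's EOT Visit" because IMP has already been discontinued.

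**Working it through.** **Inputs.** Dosing is every two weeks from Week 0. Open-label dosing starts at Week 16. EOT is Week 28 for US responders and Week 20 for US non-responders, and EOS is 8 weeks after EOT. The nominal study day is 1 + 7 × week, so Weeks 16, 18, 20, 26 and 28 are Days 113, 127, 141, 183 and 197. The SAP (section 2.7.1) defines Period B exposure as last open-label dose − first open-label dose + 14 days.

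**1. Reproduce the plan's figure.** Weeks 0, 2, …, 26 give 26/2 + 1 = 14 doses: 8 before Week 16 and 6 from Week 16. This matches section 4.1, Table 6 and the 14 marks in the US row. The row has 19 cells, as many as the header has columns, and other rows (for example Call IRT) are marked under EOT. The blank EOT cell is therefore not an effect of text extraction.

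**2. Period B exposure as planned.** 183 − 113 + 14 = 84 days, or 12 weeks, as the protocol states.

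**3. Footnote w taken literally.**

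| US group | Last dose, rest of protocol | Total IMP doses | Last dose, footnote w | Total IMP doses | Active doses if started on placebo |
|---|---|---|---|---|---|
| Week 20 responder | Week 26 | 14 | Week 28 | 15 | 7 instead of 6 |
| Week 20 non-responder | Week 18 | 10 | Week 20 | 11 | 3 instead of 2 |

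Period B exposure would become 197 − 113 + 14 = 98 days (14 weeks instead of 12) for responders. For non-responders it would become 141 − 113 + 14 = 42 days, against 127 − 113 + 14 = 28 days (6 weeks instead of 4).

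**4. The Synopsis line that runs to Week 28.** Its Period A counterpart ends at Week 14, which is the last dosing visit of that period. By parallel, the Period B line can be read as allowing a Week 28 dose. But the same line gives up to 12 weeks of treatment, and Table 6 equates 12 weeks with 6 doses, which are Weeks 16 to 26. A Week 28 dose would make 7 doses and 14 weeks. The line is loosely worded and does not establish a Week 28 dose.

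**The case against.** The strongest reply is that the protocol already settles the point. The design text and the US-specific section 10.8.2 are explicit, the EOT cell is blank, and kits are allocated centrally by the IRT (although the documents do not say how it is programmed for EOT). That stands as to likelihood: actual misdosing is improbable. It does not make the footnote correct.

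The documents do not support four stronger readings that a reader might infer:

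- **That every other statement disagrees with footnote w.** The Period B regimen line in the Synopsis does not. Section 6.3, which has participants on active treatment from Week 16 to Week 28, describes the period and not the last dose. The contradiction is with every *explicit* statement of the last dosing visit.
- **That every US participant would exceed the dose limit.** Non-responders would have 11 doses. The Synopsis limit, "Participants will not be expected to receive more than 14 doses of SAR442970", counts active drug, so a responder who started on placebo (7 active doses) would stay within it. The excess for that participant is over the total IMP count in section 4.1 and Table 6.
- **That the footnote creates a gap in safety follow-up.** AE collection ends at EOS (section 8.4.1), while the treatment-emergent period runs to 75 days after the last dose (SAP section 2.1). For responders, EOS is nominally 253 − 183 = 70 days after the Week 26 dose, already 5 days short. A Week 28 dose would make it 253 − 197 = 56 days, or 19 short. Visit windows (±3 days at dosing visits, ±5 at EOS) move both figures. The footnote would widen an existing gap, which is a separate matter.
- **That efficacy is compromised.** The extra dose would fall at Week 20 or Week 28, after the Week 16 endpoints.

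**Conclusion.** The point holds. Footnote w is wrong as written, and it is current text on the IMP row. Its size is one extra dose per affected US participant: 15 instead of 14 for responders, and 11 instead of 10 for Week 20 non-responders, the latter against an explicit ban. These counts assume nominal visit timing, no missed doses and literal compliance with the footnote. The documents do not give the number of US participants, so the total effect cannot be sized. Sample size and the Week 16 analyses are untouched. This is a minor consistency correction to a dosing instruction.

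**What to change.** End footnote w along these lines: *up to the visit before the participant's EOT visit (Week 26 for Week 20 responders, Week 18 for Week 20 non-responders); no IMP is given at the EOT visit.* This follows the Synopsis and section 10.8.2. Because it sets an upper limit, it also fits early discontinuers whose last dose came before the immediately preceding visit.

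In the Synopsis, under Study interventions, change the end of the Period B regimen from Week 28 to Week 26, so that it ends at the last dosing visit as the Period A line does.

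The cost is a rewording of one footnote and one week number. Design, sample size and analysis do not change.
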